5.2 Inclusion/Exclusion Criteria

Inclusion Criteria:

Must have physician or psychiatrist authorization form confirming participant fulfills 4 criteria:

- has diagnosis of Bipolar I or II
- has been stable and consistent with medication for last 3 months
- is in a euthymic, rather than manic or depressive, state
- is appropriate for a group-based intervention

Exclusion criteria:

- Not a native English speaker
- Less than 12 years education
- Additional psychiatric diagnosis

6 STUDY PROCEDURES/EVALUATIONS

6.1 Study Procedures

- Screening Session: A research assistant will conduct screening procedures over the phone including a brief medical questionnaire covering their history, current medications and any pre-existing conditions. Prior diagnosis of bipolar disorder and euthymic state will be confirmed with study psychiatrist. Additionally, given that the participant meets the requirements covered by the phone screen, participants will be asked to come to the Center for BrainHealth to complete further cognitive assessments.
- Cognitive Testing Session: A clinician from the Center for BrainHealth will administer a group of standardized and experimental tests to each participant for each of the cognitive testing sessions. This session may last up to 4 hours, depending on the pace of the participant's response times. The intent of the tasks is to assess higher level thinking skills, working memory, and selective learning. The cognitive test battery will include tests like Delis-Kaplan Executive Function System (DKEFS) Color-Word Interference Test, Delis-Kaplan Executive Function System (DKEFS) Card Sorting Test, Test of Strategic Learning (TOSL), Auditory Selective Learning, Wechsler Memory Scale (WMS-III) Logical Memory Subtest, Verbal Problem Solving, Wechsler Adult Intelligence Scale (WAIS) Similarities Subtest, Rey-Osterrieth Auditory Verbal Learning Test (RAVLT), Trails A, Trails B, the Controlled Order Word Association Test (COWAT), Wechsler Memory Scale (WMS-III) Digits forward and backwards, and Framing task.
- fMRI: Participants who qualify for the imaging portion will lie in the scanner while images of their brain will be recorded. Each session will take up to 90 minutes. During the MRI and during the DTI (diffusion tensor imaging) the patient will be asked just to lie still.
- Cognitive reasoning training: The gist-based reasoning training will be delivered in one, two hour session each week over 4 weeks. The strategy instruction is hierarchical and dynamically interdependent, with each strategy building upon previous strategies to transform the concrete meaning into abstracted gist-based meanings through reasoning and inference. Constructing meaning at a higher level of abstraction promotes learning which is more efficient and long lasting.
- Post Intervention: Following the intervention, patients will repeat the cognitive assessment and fMRI identical to the pre-training assessment. Participants are not paid for any of these tests or training sessions.

7 STATISTICAL CONSIDERATIONS

7.1 Study Outcome Measures

Outcome measures include behavioral measures of cognitive function and resting state brain imaging.

7.2 Sample Size Considerations

We piloted n=27 participants and 12 of those who completed brain imaging. This was a sufficient sample size to conduct a pilot-study analysis of cognitive and brain changes in this patient population pre-post reasoning training.

7.3 Participant Enrollment and Follow-Up

We enrolled 27 participants at baseline and all 27 completed the study. 12 of the 27 also completed brain imaging.

7.4 Analysis Plan

Statistical analysis plan:

General linear models will be used to assess mean changes cognitive outcomes. In resting state fMRI analysis, we will first identify the spatial extent and BOLD signal time course of the default mode network and central executive network for each subject at each time point (pre- and post-training) using advanced statistical methods like ICA. Then, we will compare networks activation across the two time points of the study using repeated measures general linear modeling. Map-wise corrected false positive rates will be controlled at .05 by Bonferroni correction.

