4 STUDY DESIGN

Participants will only include people who are fluent speakers of English, as not all of the standardized and experimental cognitive tests have been normed for non-English speakers. Participants will be screened for significant medical, neurological, or psychiatric illness other than bipolar disorder. Additionally, two separate cognitive testing and two MRI imaging procedures will be conducted with each participant: one at baseline prior to cognitive training, the second at the end of cognitive training (4 weeks). These testing procedures are explained below.

Each participant will receive an appointment card/schedule of appointments to help them keep track of what is expected of them. During the training program participants will make 1 visit per week for 2 hours each over a 4-week period. Prior to cognitive training, participants' baseline gist and detail processing ability, will be obtained with a battery of cognitive measures.

Structural and functional brain measures will also be obtained. All measurements will be taken again at the endpoint of training. Training effects will be measured behaviorally in trained areas (reasoning & physical) and untrained cognitive areas. Additionally, structural and functional brain imaging will measure changes in cerebral blood flow, global and regional brain volume, white matter tracts, efficiency, activation patterns, and blood oxygenation with a particular focus on changes to frontal regions.

5 Study Population

Our study population for this pilot study will include 20-30 adults diagnosed with bipolar disorder I or II; they will be referred by local treating psychiatrists.

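### Section 7.4 applies Bonferroni to two brain-network maps without stating the unit or family of tests, and voxel-wise it grows needlessly conservative as maps get smoother

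*Combined protocol and SAP*

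**What the plan says.** Section 7.4 (Analysis Plan) sets out the resting-state analysis in three steps.

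- By methods such as ICA, it identifies the "spatial extent and BOLD signal time course of the default mode network and central executive network for each subject at each time point".
- Then "we will compare networks activation across the two time points of the study using repeated measures general linear modeling".
- Last comes the only multiplicity rule for imaging: "Map-wise corrected false positive rates will be controlled at .05 by Bonferroni correction".

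No divisor is given. Section 7.1 says only that outcomes include cognitive measures and resting-state imaging. Section 7.3 gives the imaging sample: "12 of the 27 also completed brain imaging".

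**The concern.** A Bonferroni rule is defined by its divisor, and this one has none. The reader is not told whether a test is a voxel, a region or a network summary, how many tests there are, or whether the two networks share one .05. Nor does the text fix the voxel set: each network's extent is found separately for each subject at each time point, and no common mask is named.

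Two things follow on the most natural reading, voxels within each map. First, a change reported in either network carries a joint false positive risk that may exceed 5%, and the plan does not say whether that is intended. Second, Bonferroni treats neighbouring voxels as if they carried separate information. In smoothed images they do not, so with 12 people the rule can discard regional changes that a test using the map's own correlation would keep at the same error rate.

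**Working it through.** **Inputs from the documents.** Level .05, Bonferroni and two networks (section 7.4); 12 people imaged (section 7.3).

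**Assumed, because the documents do not give them.** One two-sided pre-post contrast per network; 12 complete pre-post pairs; 22 × 22 × 22 = 10,648 voxels per map; smoothness (FWHM) of 1.6, 3.5, 7.1 or 10.6 voxels; two independent maps; a true change of 1 SD of the paired differences in a 123-voxel sphere.

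**1. The plan's own figure.** With V tests in a map, each at .05/V, the bound is V × (.05/V) = .05 for any V. The map-wise .05 is reproduced.

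**2. Error over both networks.**
- Per-map family: bound .05 + .05 = .10. If the maps are independent and each uses its full .05, the error is 1 − .95² = .0975.
- Joint family, .05/(2V) per test: bound 2V × .05/(2V) = .05. If the maps are independent and each uses its full .025, it is 1 − .975² = .0494.

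**3. How much the unit matters.** Two-sided paired t, 11 degrees of freedom, noncentrality √12 for a 1-SD change at the tested unit:

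| Tests in divisor | Critical t | Power at one given test |
|---|---|---|
| 2 (one summary per network) | 2.593 | 79% |
| 1,000 | 6.412 | 4.4% |
| 10,648 | 8.281 | 0.75% |
| 50,000 | 9.701 | 0.2% |

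The rows are not like for like. The first supposes that the whole network summary moves by 1 SD; the others concern one voxel, where power is lower than for detecting any voxel of a region.

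**4. Simulation: chance of any false positive over both networks.** Gaussian-smoothed null maps, 12 pairs, 1,757 / 1,284 / 876 / 851 runs by smoothness. Sign-flipping uses all 2¹² = 4,096 patterns.

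| Rule | FWHM 1.6 | 3.5 | 7.1 | 10.6 |
|---|---|---|---|---|
| Bonferroni per map | 8.9% | 7.6% | 2.2% | 0.7% |
| Bonferroni over both maps (t 8.896) | 4.6% | 4.1% | 0.7% | 0.5% |
| Joint sign-flip max-t | 4.7% | 4.8% | 4.2% | 4.0% |

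**5. Simulation: detecting at least one voxel of the 123-voxel region.**

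| Rule | FWHM 1.6 | 3.5 | 7.1 | 10.6 |
|---|---|---|---|---|
| Bonferroni per map | 53% | 27% | 10% | 4% |
| Bonferroni over both maps | 36% | 18% | 7% | 3% |
| Joint sign-flip max-t | 36% | 21% | 15% | 14% |

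The like-for-like comparison is the last two rows, which share a family. From the unrounded rates the ratios are .364/.359 = 1.0, .210/.179 = 1.2, .145/.066 = 2.2 and .136/.033 = 4.1. Monte Carlo standard errors are 0.2 to 0.8 points for error and 0.4 to 1.2 points for detection.

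**The case against.** The strongest reply is that the plan promises control per map and Bonferroni delivers it at any voxel count. That stands. A reader might infer that the plan claims .05 over both networks and misses it. The documents do not support this: they make no joint claim, the 10% is a ceiling, and a family spanning both maps would hold .05. In the smooth simulated maps the joint error under the per-map rule is only 2.2% and 0.7%.

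A second reply is that the wording is less open than it looks. A map-wise correction most naturally means tests within a map, and one summary per network is not a map. A voxel-level repeated-measures model also implies a common voxel set at both times. Both points are fair: the voxel reading is the more likely one, but it has to be inferred.

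Third, Bonferroni is valid, and one clause naming the unit and family would remove the ambiguity. That is true of the ambiguity. It would not recover the detection lost in smooth maps, which is the reason to change the method. The size of that gain, however, rests on assumed smoothness and on independent maps, although both networks come from the same people.

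Finally, this is a single-arm pilot. The imaging objectives named in the synopsis and section 3 are blood flow and its correlation with behaviour, not BOLD network activation. That limits the weight of the point.

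**Conclusion.** The point holds in a limited form. Section 7.4 leaves the unit and family of its Bonferroni rule unstated. On the voxel-within-map reading the stated .05 per map is met, and the error over both networks is bounded by 10%; that bound needs only one contrast per network. On the same reading the rule becomes needlessly conservative as maps get smoother. At an equal joint family, sign-flip max-t keeps the error near 4 to 5% and detects the assumed region about as often in rough maps and about 2 to 4 times as often in smooth maps.

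The error and detection percentages rest on the assumed voxel count, smoothness, region, effect, map independence and 12 complete pairs. The omission does not. A reader might also infer that the trial's main result is at risk; it is not, since only the BOLD network comparison is concerned. A revision is worth making, with medium confidence in the size of the benefit.

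**What to change.** Replace the last sentence of section 7.4 with a statement that:

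- names the voxel as the unit and fixes one voxel set for both time points without using the pre-post difference, for example from the pre-post average, which sign flips leave unchanged;
- tests by two-sided sign-flip max-t at .05, using all 4,096 sign patterns if there are 12 complete pairs;
- says whether the family is each map or both networks jointly (a joint family holds .05 over both);
- says whether these choices were made before or after the difference maps were seen.

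If the intended unit is one summary per network, test each at .025 and report a 97.5% confidence interval, with half-width 2.593/√12 = 0.75 SD at n = 12. This gives up localisation and suits only a network-wide change: for the 123-voxel region (123/10,648 = 1.2% of the network) the network mean detected it in 11/3/1/2% of runs.

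The cost is new SAP wording and a re-analysis of existing scans, with no new data. Sign-flipping assumes that the paired differences are symmetric about zero under the null. If a joint family replaces per-map control, detection falls in rough maps (53% to 36%, 27% to 21%) because the joint error comes down from 8.9% and 7.6% to just under 5%. It rises in smooth maps (10% to 15%, 4% to 14%).

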8 SUBJECT CONFIDENTIALITY

The study protocol, documentation, data and all other information generated will be held in strict confidence. No information concerning the study or the data will be released to any unauthorized third party without prior written approval of the sponsor.

Personally identifiable information (PII) was removed at study closure; de-identified data collected within the online dashboard will remain there. Additionally, participants in this pilot will have the option to consent into the larger BrainHealth Project study and carry forward their pilot data at the end of pilot study.

9 INFORMED CONSENT PROCESS

Informed consent is a process that is initiated prior to the individual's agreeing to participate in the study and continuing throughout the individual's study participation. Extensive discussion of risks and possible benefits of participation in this study will be provided to the subjects. Consent forms describing in detail the study procedures and risks are given to the subject and written documentation of informed consent is required prior to enrolling in the study. Consent forms will be IRB approved and the subject will be asked to read and review the document. Upon reviewing the document, the investigator will explain the research study to the subject and answer any questions that may arise. The subjects will sign the informed consent document prior to being enrolled in the study. The subjects may withdraw consent at any time throughout the course of the study. A copy of the informed consent document will be given to the subjects for their records. The rights and welfare of the subjects will be protected by emphasizing to them that the quality of their medical care will not be adversely affected if they decline to participate in this study.

